### **3.3. Treatments**

During the OLE, all subjects will receive 15 mg losmapimod BID open-label.

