### 8.1. MSK MRI Muscle Fat Fraction, Lean Muscle Volume and Muscle Fat Infiltration

Measurement of the extent of skeletal muscle tissue replacement by fat in FSHD patients will be done through automatic skeletal muscle segmentation for the 3D muscle volumes and fat fraction analysis via robust algorithms using Dixon imaging. Schedule of MRI assessments are described in [Appendix 14.2](#).

**A. Longitudinal composite measures:** Longitudinal whole-body composite variables, incorporating pre-selected muscles, will be derived for longitudinal analysis of muscle fat fraction, lean muscle volume and muscle fat infiltration ( $MFF_{tot}$ ,  $LMV_{tot}$ , and  $MFI_{tot}$  respectively), as described in [Appendix 14.1](#). The scores will be derived by scientists at the MRI Service Provider (AMRA Medical Inc.).

The longitudinal composite observations of relative change in  $LMV$  is sensitive to low overall  $LMV$ . Therefore, a criterion is required for exclusion of such observations. To ensure that the relative change in  $LMV$  is reliable,  $LMV_{ref}$  ( $LMV$  at reference timepoint) needs to fulfill one of the below:

- Be at least 25 cl and consist of measurements from at least 2 muscles combined.
- Be at least 50 cl with measurements from at least one muscle.

Further, if the subject's individual muscles fulfill neither criteria, the change from reference timepoint in longitudinal composite scores for  $LMV$  (L),  $LMV$  (%),  $MFF$  (%), and  $MFI$  (%) are set to missing. If the individual muscles could fulfill at least one of the two bullets above, the change from reference time point in longitudinal composite scores for  $LMV$  (L),  $LMV$  (%),  $MFF$  (%), and  $MFI$  (%) are not set to missing.

For each treatment sequence/entry point of OLE, descriptive statistics of  $MFF_{tot}$ ,  $LMV_{tot}$ , and  $MFI_{tot}$  per visit as well as changes from baseline will be presented.

To assess the efficacy of losmapimod in the placebo group after rollover into the OLE and the durability of efficacy in the losmapimod group, the mean change from baseline (+- SE) by visit of  $MFF_{tot}$ ,  $LMV_{tot}$ , and  $MFI_{tot}$  will be graphically presented over both the placebo-controlled treatment period and OLE.

Three types of % change/year in longitudinal composite scores will be estimated:

- (1) % change/year for losmapimod using data from both the placebo-controlled treatment period and OLE

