Data while the subject is on losmapimod will be considered in the analysis. For subjects who were randomized to losmapimod at baseline, data from both the placebo-controlled treatment period and OLE will be included in the analysis. For subjects who were randomized to placebo and transitioned to losmapimod at OLE, their data under losmapimod are considered in the analysis. A linear mixed-effects model will be used to analyze the longitudinal composite scores for each treatment sequence, with intercept and time as random effects, and with adjustment for repeat number category and region (EU, USA, and Canada). An unstructured covariance matrix will be used to model the correlations between repeated measurements within each subject. In addition, the % change/year will be presented and will be derived as  $[(\text{slope}/\text{baseline}) * (365/T) * 100]$  where baseline is the LS mean of the intercept and T is the duration of treatment with losmapimod minus 1.

- (2) % change/year for the losmapimod group and placebo group using data from the placebo-controlled treatment period for subjects who completed 48 weeks of treatment in the placebo-controlled treatment period

A linear mixed-effects model will be used to analyze the longitudinal composite scores, with treatment sequence as a fixed effect, and intercept, time and treatment sequence-by-time interaction as random effects, adjusting for repeat number category and region (EU, USA, and Canada). An unstructured covariance matrix will be used to model the correlations between repeated measurements within each subject. Within-treatment sequence LS mean of slope and the associated SE, intercept and the associated SE, difference in the LS mean of slope and the associated 2-sided 95% CI and 2-sided p-value will be derived from the linear mixed-effects model and will be provided in the summary table. In addition, the % change/year will be presented. It will be derived as  $[(\text{slope}/\text{baseline}) * (365/T) * 100]$  where baseline is the LS mean of the intercept and T is the duration of treatment with study drug minus 1. Difference in % change/year between treatment sequences will also be presented.

- (3) % change/year for each treatment sequence using data from the OLE for subjects who completed 48 weeks of treatment in the placebo-controlled treatment period

The same approach as in (2) will be used to analyze the longitudinal composite scores in the OLE.

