In estimating the three types of % change/year, if any model using an unstructured covariance matrix does not converge, an AR(1) covariance structure will be used

instead. If either unstructured or AR(1) covariance matrix does not lead to a convergent model, a compound symmetric covariance structure will be used instead.

The purpose of estimating % change/year for each treatment sequence in (2) and (3) above is to explore the possibility that earlier treatment with losmapimod is better than delayed treatment and that the placebo group's progression slows after treatment with losmapimod.

The change from baseline in the composite parameters will also be summarized by subgroups identified in [Section 4.7](#) to evaluate consistency of treatment effects across the subgroups.

- B. **Individual Muscles:** For each muscle location, a similar method will be used to analyze muscle fat fraction (%), lean muscle volume (L), and muscle fat infiltration (%) per visit as well as changes from baseline.
- C. **Cross-sectional composite measures:** The cross-sectional composite scores will be used to correlate the results with Clinical Outcome Assessments (i.e., TUG, FSHD TUG and RWS). The convention that will be used to get extremity equivalent of the cross-sectional results is provided in [Table 8-1](#).

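### SAP 8.1 gives estimates (2) and (3) two purposes, early versus delayed start and slowing after the switch, but plans no matching contrast with a valid confidence interval for either

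*SAP*

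**What the plan says.** SAP 8.1 plans three annualised changes for the MRI composites. Two matter here:

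- Estimate (2) is the % "change/year for the losmapimod group and placebo group using data from the placebo-controlled treatment period", in subjects who completed 48 weeks.
- Estimate (3) is the % "change/year for each treatment sequence using data from the OLE for subjects who completed 48 weeks of treatment". For its model the SAP says: "The same approach as in (2) will be used to analyze the longitudinal composite scores in the OLE".

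Each is a separate linear mixed model on one period's data. Each reports slope and intercept with SE by sequence. The only contrast given inference is between sequences: "difference in the LS mean of slope and the associated 2-sided 95% CI and 2-sided p-value will be derived". A between-sequence difference in % change/year is also presented, with no interval mentioned.

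The SAP states two purposes for the pair: to "explore the possibility that earlier treatment with losmapimod is better than delayed treatment", and to explore whether "the placebo group's progression slows after treatment with losmapimod". SAP 3.3 fixes the treatment in the second period: "During the OLE, all subjects will receive 15 mg losmapimod BID open-label".

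There is also a descriptive display. "To assess the efficacy of losmapimod in the placebo group after rollover into the OLE and the durability of efficacy in the losmapimod group", mean change from baseline with SE is plotted by visit over both periods. SAP 4.4 computes OLE changes from the original baseline as well as from the OLE baseline. Sections 8.2.1 to 8.2.3 reuse the slope approach for reachable workspace (RWS), classic TUG and dynamometry.

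**The concern.** A delayed-start question is about level: does the group that started earlier still have more muscle once both groups are treated? A slope comparison within the OLE asks something else, namely whether the two groups progress at different rates on the same drug. If the drug slows decline by the same amount whenever it starts, the answer to the first is yes and to the second is no.

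Slowing after the switch is a within-subject change of slope in the Placebo/Losmapimod sequence. Its two slopes come from separate models fitted to the same people, so they are correlated, and the plan gives no SE or CI for their difference.

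At stake is interpretation. A near-zero OLE slope difference with a large p-value could be reported as no advantage of early treatment when it is what a constant, lasting benefit would produce.

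**Working it through.** The documents give no effect size, variance or power for these comparisons, so there is no figure to reproduce.

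**Inputs from the documents.** 80 enrolled (SAP 4.8); 12 rolled over at Week 24 (Protocol 3.1.1) and fall outside (2) and (3), leaving at most 80 − 12 = 68. MRI at screening, Weeks 12 and 48 (Protocol 3.1.1), then Weeks 72, 96, 120 and 144 (SAP Appendix 14.2).

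**Assumptions.** 34 per sequence, complete scans to Week 144, screening taken as Week 0; index 100 at baseline; decline 3 points/year on placebo and 1.5 on losmapimod; between-subject slope SD 1.5/year; residual SD 1.5.

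**1. What each contrast equals.** The controlled period lasts 48/52 = 0.923 year; Week 48 to Week 144 is 96/52 = 1.846 years. The gap at Week 48 is 1.5 × 0.923 = 1.38 whenever the drug works in the early group. Gap at Week 144 = 1.38 + (OLE slope difference) × 1.846, except for the step.

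| Scenario | (2) slope diff | (3) slope diff | Gap, Week 144 | Placebo/Losmapimod slope change |
|---|---|---|---|---|
| No effect | 0 | 0 | 0 | 0 |
| Equal effect whenever started, lead kept | +1.5 | 0 | +1.38 | +1.5 |
| Same, lead erased by a step at the switch | +1.5 | 0 | 0 | +1.5 |
| Gradual catch-up (delayed OLE slope −0.75) | +1.5 | −0.75 | 0 | +2.25 |
| Lead widens (delayed OLE slope −2.25) | +1.5 | +0.75 | +2.77 | +0.75 |
| Works only if started early (delayed OLE slope −3) | +1.5 | +1.5 | +4.15 | 0 |

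The zero in (3) under a kept lead does not depend on the assumed values. Rows 2 and 3 agree on both (2) and (3) and differ only in the gap, so even the pair does not measure the lead that remains.

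On the % change/year scale, with the intercept taken at OLE start, row 2 is not exactly zero: −1.5/98.62 against −1.5/97.23, or −1.521% against −1.543%, a difference of 0.02 points caused by the denominators.

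**2. Precision of (3).** SE = √[2(1.5² + 1.5²/S)/34], where S is the sum of squared deviations of scan times in years.

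- Weeks 72 to 144: S = 1.065, SE = 0.51.
- Counting the Week 48 scan as OLE data: S = 2.130, SE = 0.44. SAP 4.1 starts the OLE the day after Week 48, so 0.51 is closer to the text.

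Under both no effect and a kept lead the expectation is 0 and rejection about 5%. If the drug works only when started early, the expected difference is 1.5 and power is about 84% (SE 0.51) to 93% (SE 0.44).

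**3. SE of the slope change.** S is 0.4615 for Weeks 0, 12 and 48. With a common subject slope across periods, that slope cancels in the within-subject difference:

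- Paired: √[2.25 × (1/0.4615 + 1/1.065)/34] = √(6.99/34) = 0.45.
- Combining the two SEs as if independent: √[(2 × 1.5² + 6.99)/34] = 0.58. With slope SD 2 or 4 this becomes 0.66 or 1.07, while the paired value stays at 0.45.

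Subtraction therefore gives the right point estimate, but the reported SEs do not give its interval.

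**4. One two-phase model on the same data** (generalised least squares, random intercept and slope, normal-approximation power, kept-lead scenario):

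- Within-placebo slope change: 1.5, SE 0.45, power about 91%.
- That change net of Losmapimod/Losmapimod: 1.5, SE 0.45 × √2 = 0.64, power about 65%.
- Week 96 level difference: 1.38, SE 0.75, power about 45%.

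**The case against.** The best defence is that the SAP assigns the purposes to (2) and (3) jointly. Under a real effect (2) is non-zero, so the pair separates no effect from a working drug. That stands. The pair still cannot tell a kept lead from an erased one, because (2) is drug versus placebo.

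A reader might infer that the placebo group's slowing is never estimated. The documents do not support that: its slope is reported with SE in each period, and the change follows by subtraction. Only a valid SE or CI for the change is missing.

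A reader might also infer that (3) is useless, or that zero is its expected value whenever the drug works. That is too strong. If early start is better because the drug works only, or better, when started early, (3) is a suitable contrast and can be well powered.

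The level gap is not hidden either. By-visit means with SEs are planned by sequence from the original baseline. The sequences are separate groups, so an unadjusted difference and interval can be worked out by hand. What is not planned is an adjusted between-sequence estimate with a CI.

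The aim is exploratory, the OLE's primary objective is safety, and Protocol 2.2.2 lists only plasma concentrations as the OLE secondary objective. No alpha depends on (2) or (3), so nothing here bears on type I error or on the controlled-period conclusions.

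**Conclusion.** The point holds as a mismatch between stated purpose and planned contrast. Neither the early-versus-delayed question nor the slowing question has a contrast with a valid CI. A lasting, equal benefit gives zero in (3), the same value as no effect or a lead erased by a step; gradual catch-up gives a negative value that favours delay.

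The zero is algebra and does not rest on the illustration. The SEs and powers do. They assume that all 68 remaining subjects roll over, split evenly, with complete scans to Week 144. Protocol Figure 1 notes that Week 12 MRI may not have been possible, and SAP 3.1 says efficacy data are collected only until protocol version 5.0 is executed. The powers are therefore a best case for those effect sizes and SDs.

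The change is worth making because the SAP names these questions itself and attaches a p-value to a contrast that a reader could take as the answer.

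**What to change.** Keep (2) and (3). For the same subjects, add one linear mixed model over both periods with a knot at the first open-label dose, separate fixed slopes by sequence and phase, and the covariates already planned. Report with 95% CI:

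- (a) the between-sequence difference in change from original baseline at a named OLE visit, for example Week 96, for early versus delayed start;
- (b) OLE slope minus controlled-period slope within Placebo/Losmapimod, for slowing after the switch;
- (c) contrast (b) minus the same contrast in Losmapimod/Losmapimod, to remove period and practice effects.

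State in 8.1 that a zero OLE slope difference in (3) indicates parallel progression and is not evidence against early treatment.

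Apply this to the MRI composites and to the main summaries of RWS, classic TUG and dynamometry. Extending it to every RWS measure would mean 8 areas × 2 weight conditions × 3 arm summaries = 48 models, which is not needed.

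The cost is SAP wording, extra models and some table rows, on data already in the plan. The new contrasts remain exploratory. With about 45% power for (a) and 65% for (c) under the assumed values, they should be reported as estimates with intervals and not judged by significance; otherwise (a) could be misread in the same way as (3).

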**Table 8-1. Extremity Equivalent of MRI Cross-sectional Results.**

MRI Cross-sectional Results	Equivalent Extremity
TUG Cross-sectional	Lower extremity (LE)
FSHD TUG	All Muscles
RWS Dominant Cross-sectional	Dominant upper extremity
RWS Non-Dominant Cross-sectional	Non-Dominant upper extremity

The muscles considered for each of the cross-sectional composite scores are presented in [Table 8-2](#).

**Table 8-2. Muscles Considered in the MRI Cross-sectional Scores**

Test	Muscles		
	Upper Extremity	Trunk	Lower Extremity
FHSD TUG	Supraspinatus Infraspinatus	Pectoralis Major Rhomboideus	Quadriceps Hamstrings

Test	Muscles		
	Upper Extremity	Trunk	Lower Extremity
	Subscapularis Teres Minor Deltoid Biceps Brachii Triceps Brachii	Latissimus Dorsi & Teres Major Trapezius Serratus Anterior Paraspinal (C3-Sacrum)	Adductors Tibialis Anterior Gastrocnemius Medialis
Classic TUG	N/A	N/A	Quadriceps Hamstrings Adductors Tibialis Anterior Gastrocnemius Medialis
RWS	Supraspinatus Infraspinatus Subscapularis Teres Minor Deltoid Biceps Brachii Triceps Brachii	Pectoralis Major Rhomboideus Latissimus Dorsi & Teres Major Serratus Anterior	N/A

Spearman correlation coefficients will be used to assess relationships between the cross-sectional composite scores and classical and FSHD TUG and RWS results by visit. The Spearman correlation coefficient and p-value will be calculated and presented in a table. This will also be graphically presented using scatterplots. Specifically, the following relationships will be assessed:

- All muscles vs. FSHD-TUG
- LE vs. Classical TUG
- Dominant upper extremity vs. Dominant RWS
- Non-Dominant upper extremity vs. Non-Dominant RWS

## 8.2. Clinical Outcome Assessments

### 8.2.1. Reachable Workspace With and Without Weights

The reachable workspace (RWS) is a 3-dimensional sensor-based system (using a single depth-ranging sensor) that can unobtrusively detect an individual's ability to reach in various directions above and below the shoulder, and reflects an individual global upper extremity

function. The evaluation will be performed with and without weights and on both the right and left arms. Schedule of RWS assessments are described in [Appendix 14.2](#).

The absolute total RWS surface envelope area ( $m^2$ ) as well as areas for each of the quadrants will be calculated and provided by a vendor with no access to treatment assignment information from the placebo-controlled treatment period of the study. The reachable workspace relative surface area (RSA) represents the portion of the unit hemisphere that is covered by an individual's arm movement.

For each treatment sequence/entry point of OLE, descriptive statistics of RSA results per visit as well as the change from baseline will be presented by quadrant, upper quadrants (Q1+Q3), total area with Q5 (Q1+Q2+Q3+Q4+Q5), and total area without Q5 (Q1+Q2+Q3+Q4) for the assessment with weights and without weights, and by dominant arm, non-dominant arm and average from two arms. Similar methods will be used to analyze the change from baseline in RSA for all RSA measures. For upper quadrants, total area with Q5 and without Q5, the average results from two arms will be calculated as:

- first calculate the sum on each arm,
- then calculate the average from two arms.

If results are missing on one arm and non-missing on the other arm, the average result will be equal to the non-missing result from one arm.

To assess the efficacy of losmapimod in the placebo group after rollover into the OLE and the durability of efficacy in the losmapimod group, the mean change from baseline (+ SE) by visit of all RSA measures will be graphically presented over both the placebo-controlled treatment period and OLE.

Three types of % change/year in RSA will be estimated. The analysis approaches will be similar to those of the MRI longitudinal composite scores in Section 8.1. Separate models will be run for each quadrant (Q1, Q2, Q3, Q4 and Q5), upper quadrants (Q1+Q3), total area with Q5 (Q1+Q2+Q3+Q4+Q5), and total area without Q5 (Q1+Q2+Q3+Q4) with and without weights, and for the dominant arm, non-dominant arm and average from two arms.

Invalid RWS data points due to software issues will be flagged and excluded from all analyses.

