1. INTRODUCTION

1.1. BACKGROUND

Facioscapulohumeral muscular dystrophy (FSHD) is a rare disabling disease with an estimated worldwide population prevalence of between 1:15,000 and 1:20,000 (Statland and Tawil, 2014), or approximately 16,000 to 21,000 affected individuals in the United States. A higher prevalence rate of 12/100,000 was reported in a population-based study in the Netherlands (Deenen et al, 2014). About two-thirds of cases are familial-inherited in an autosomal dominant fashion, and one-third are sporadic. FSHD is characterized by descending progressive skeletal muscle weakness affecting the face, shoulders, arms, and trunk, followed by weakness of the distal lower extremities and pelvic girdle. Symptoms typically first appear later in the second decade of life but can begin at any age (Tawil et al, 2015). Most cases present with shoulder girdle weakness, which is eventually found in nearly all patients (Padberg, 1982). Muscle biopsies show myopathic or dystrophic changes, including variability in fiber size, rounded fibers, central nuclei, necrotic or regenerating fibers, increased connective tissue, and fatty deposition. Up to one-third of muscle biopsies show a lymphocyte-predominant perivascular inflammatory infiltrate (Statland et al, 2015b). Muscle strength, as measured by quantitative muscle testing, decreases at an average rate of 1% to 4% per year (Statland and Tawil, 2014). The most frequent newly developed functional motor limitations include difficulty getting up from lying down in bed and difficulty using arms for activities of daily living (Statland and Tawil, 2014). The 6-year risk of wheelchair use is 24% (Statland et al, 2015a). All quality of life domains on the 36-Item Short Form Health Survey are significantly impaired, and over half of patients with FSHD report at least mild to moderate pain (Moris et al, 2018; Padua et al, 2009). Asymmetry of muscle involvement is common. Cardiac muscle is spared, and respiratory muscles are involved in a minority of patients.

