3.1.1. Placebo-Controlled Treatment Period

During the placebo-controlled treatment period, a total of approximately 76 subjects with FSHD1 will be randomized 1:1 to receive 15 mg PO of losmapimod (n=38) or placebo (n=38) tablets BID for 48 weeks.

At the time of this protocol amendment (10 April 2020), enrollment was completed. A total of 80 subjects have been enrolled. Twelve subjects had rolled over to the OLE portion of the study at Week 24, prior to the COVID-19 pandemic (under protocol version 3.0). At their next clinic visits, these 12 subjects will follow the assessments for the Week 36 visit followed by the Week 48 visit in the placebo-controlled portion of the study under the COVID-19 Pandemic Emergency protocol version 4.0. These subjects will continue to receive open-label losmapimod during this time.

Subjects will participate in the placebo-controlled treatment period for approximately 53 weeks, including the following:

- a 4-week screening period: Day -28 until Day -1 before the first study drug administration
- a 48-week placebo-controlled treatment period
- for subjects who choose not to roll over into the OLE, a safety follow-up visit 7 days (± 3 days) after the last dose of study drug (OLE visits and procedures are described in Section 3.1.2)

The 12 subjects who rolled over to the OLE portion of the study at Week 24, prior to the COVID-19 pandemic (under protocol version 3.0), participated in the placebo-controlled portion of the study for approximately 29 weeks including the following:

- a 4-week screening period: Day -28 until Day -1 before the first study drug administration
- a 24-week placebo-controlled treatment period
- for subjects who chose not to roll over into the OLE, a safety follow-up visit 7 days (± 3 days) after the last dose of study drug (OLE visits and procedures are described in Section 3.1.2)

During the placebo-controlled treatment period, subjects will be asked to attend the study clinic at each scheduled visit (Table 2). Study drug (losmapimod or placebo) will be administered BID and should be taken with food.

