### **3.2.3. Exploratory Endpoints**

The exploratory endpoints of the OLE, based on protocol version 4.0, are as follows:

- Changes from baseline in COAs after long-term dosing (at every 12-week time point):
  - RWS with and without weights
  - Classic and FSHD TUG
  - Muscle strength by hand-held quantitative dynamometry
  - MFM Domain I
  - FSHD-HI
  - PGIC
- Changes from baseline in inflammatory, immune, apoptotic, and other muscle disease transcripts in circulating proteins in plasma and serum after long-term dosing (at every 24-week time point)

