#### **4.4. Baseline, Study Day, and Change from Baseline Definitions**

Unless indicated otherwise, baseline will be defined as the last non-missing evaluation on or before the day of first dose of study drug in the placebo-controlled treatment period. If the last non-missing evaluation and the study drug administration occur on the same day, timing of the evaluation will be used to determine the pre- or post-dose. If timing is not available, the evaluation is considered pre- or post-dose based on the schedule of events for that assessment. For example, AEs and concomitant medication are considered post-baseline evaluations.

For the OLE baseline, it is defined as the last non-missing evaluation before the first dose of losmapimod in the OLE.

Relative study days will be calculated as:

$(\text{assessment date} - \text{first study drug administration date}) + 1$

if the assessment date is on the same day or after the first dosing date, otherwise:

$(\text{assessment date} - \text{first study drug administration date})$ .

Where applicable, study day relative to first dose of losmapimod will also be provided and this will be calculated as:

$(\text{assessment date} - \text{first losmapimod administration date}) + 1$

if the assessment date is on the same day or after the first dosing date, otherwise:

$(\text{assessment date} - \text{first losmapimod administration date})$ .

Both study days will be presented on all listings where appropriate.

Change from baseline will be computed as (post-baseline assessment value - baseline assessment value). Percent change from baseline will be computed as  $(\text{change from baseline value} / \text{baseline assessment value}) * 100$ . For the OLE visits, change from baseline will be computed based on both baseline assessment value, baseline in the placebo-controlled treatment period and baseline in OLE.

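### The two-arm Reachable Workspace average falls back to whichever arm is available, so a difference between limbs can be read as change over time

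*SAP*

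**What the plan says.** SAP 8.2.1 measures both arms, with and without weights. For the upper quadrants and the two total areas, it sums within each arm and then averages the arms at that visit. For incomplete visits the rule is: "If results are missing on one arm and non-missing on the other arm, the average result will be equal to the non-missing result" from the arm that is present. This departs from the default in SAP 4.3, which leaves missing values missing unless the SAP states otherwise.

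The averaged measure is used in three places in SAP 8.2.1: the by-visit summaries and change from baseline, the mean-change figures, and the three annualised slope analyses. The last are run "with and without weights, and for the dominant arm, non-dominant arm and average from two arms".

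SAP 4.4 defines change in general terms: "Change from baseline will be computed as (post-baseline assessment value - baseline assessment value"). For OLE visits, "change from baseline will be computed based on both baseline assessment value, baseline in the placebo-controlled treatment period and baseline in OLE". Neither sentence mentions which arms must be present.

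Protocol 1.1 says of the disease: "Asymmetry of muscle involvement is common".

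**The concern.** A change from baseline should compare like with like. Under the fallback rule, the averaged value can be a two-arm mean at one visit and a single arm at another, or the right arm at one visit and the left at another. Subtracting these mixes a fixed difference between limbs with change over time. In a disease where asymmetry is common, that difference need not be small relative to the change of interest.

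One-arm records are foreseeable, since the SAP writes a rule for them. SAP 8.2.1 also excludes RWS data points that are invalid because of software issues, without saying whether this removes one arm or both.

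A one-arm record at a baseline visit matters most. It enters every later averaged change from that baseline, except at visits where the same arm is again the only one present. The mean-change figures are meant to show the effect after rollover from placebo and durability on losmapimod, so they are where an artefact could mislead.

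**Working it through.** The plan gives no figure for this rule, so there is none to reproduce. The rule can be applied directly.

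**Algebra.** Let a and b be the dominant and non-dominant arm values at baseline, with D = a − b. Suppose first that neither arm truly changes.
- Both arms at baseline, dominant only later: a − (a + b)/2 = +D/2. Non-dominant only later: −D/2.
- Dominant only at baseline, both later: (a + b)/2 − a = −D/2. Non-dominant only at baseline: +D/2.
- Opposite single arms: b − a = −D, or +D.
- Same single arm at both visits, or a = b: 0.

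If the arms truly change by different amounts, the first case also carries plus or minus half the difference between those changes.

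**On the RSA scale (assumed values).** With arms of 0.60 and 0.40, the baseline average is 0.50. Losing one arm later gives +0.10 or −0.10, which is 20% of baseline. Opposite arms give 0.20 in absolute size. If each arm truly falls by 0.02:
- non-dominant arm missing later: 0.58 − 0.50 = +0.08;
- dominant arm missing later: 0.38 − 0.50 = −0.12;
- change taken within the arm present at both visits: −0.02 either way.

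So the sign of the reported change can reverse.

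**As a percentage of the baseline the rule would report.** Set the stronger arm to 1 and the weaker to 1 − d, and assume d from 0.05 to 0.40.

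| Arms at baseline → later | Formula | d = 0.05 | d = 0.40 |
|---|---|---|---|
| Both → one | ±(d/2)/(1 − d/2) | ±2.6% | ±25% |
| Stronger → both | −d/2 | −2.5% | −20% |
| Weaker → both | (d/2)/(1 − d) | +2.6% | +33% |
| Stronger → weaker | −d | −5% | −40% |
| Weaker → stronger | d/(1 − d) | +5.3% | +67% |

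**Group mean at one visit, one affected subject of the first type, equal baselines assumed.** Protocol 3.1.1 reports 80 enrolled and that "Twelve subjects had rolled over to the OLE portion of the study at Week 24". SAP 4.2 splits those 12 over two sequences, about 6 each if even. At most 80 − 12 = 68 remain for the Week 48 entry groups, about 34 each.
- Week 24 entry group: 2.56%/6 = 0.43% to 25%/6 = 4.2% of baseline.
- Week 48 entry group: 2.56%/34 = 0.08% to 25%/34 = 0.74%.

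**Slope.** Protocol Table 2 schedules RWS at Day 1 and Weeks 4, 12, 24, 36 and 48. Taking these as weeks 0 to 48, the mean time is 124/6 = 20.67 weeks and the sum of squared deviations is 1,773. The shift in one subject's least-squares slope per unit of artefact, per year of 52.14 weeks, is (t − 20.67)/1,773 × 52.14:
- Week 48: 0.80;
- Week 36: 0.45;
- Week 24: 0.10.

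A Week 48 artefact of 2.6–25% therefore moves that subject's slope by 2.1–20% of baseline per year, and the mean of 34 slopes by 0.06–0.59% per year. The mixed model would shrink this.

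**Random missing arm.** The artefact is then plus or minus with equal probability, so the expected shift is 0. If a share p of subjects is affected at a visit, the added between-subject SD is √p × artefact. For p = 5–20% (assumed), that is √0.05 × 2.56% = 0.6% to √0.20 × 25% = 11% of baseline.

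**The case against.** The strongest reply is that both triggering conditions are unquantified. The protocol's remark on asymmetry concerns muscle involvement, not left–right RSA, and a software fault may well spoil a whole session. If one-arm records are rare, the effect is negligible. This stands: every percentage above is conditional.

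It is also fair that random missingness gives noise, not bias, and that the plan already limits the harm:
- SAP 3.2.3 lists RWS under a heading that begins "The exploratory endpoints of the OLE, based on protocol version 4.0, are as follows".
- Protocol 7.6.4 denies exploratory comparisons any confirmatory value.
- The dominant-arm and non-dominant-arm results are planned separately, and the MRI correlations in SAP 8.1 use single arms.
- The Week 24 entry groups, where one record weighs most, are outside the second and third slope analyses, which SAP 8.1 restricts to subjects who completed 48 weeks.
- The 0.80 slope factor is the highest in the 48-week schedule.

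These points limit the size but do not remove the mechanism: the averaged tables, figures and models remain affected. Retaining data is a reasonable aim, but the fallback retains a different quantity under the same name. The SAP is stricter for MRI: SAP 14.1 applies a tighter quality rule to longitudinal than to cross-sectional use, and SAP 8.1 sets composite changes to missing when the reference volume is inadequate.

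Two further points are partly right. SAP 4.4 takes the OLE baseline as the last non-missing evaluation and does not say whether that is chosen per arm or after averaging, so carry-forward from that baseline is less certain. It is certain for the original baseline, which has no earlier RWS assessment. The remedy also has side effects, given under the fix.

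**Conclusion.** The concern holds. When the available arms differ between the baseline and a later visit and the arms are unequal, the rule puts half or all of the between-arm difference into the averaged change, and nothing else in the documents corrects it. The mechanism is certain, but its frequency and size are unknown because the documents do not report one-arm records or RSA asymmetry.

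The practical consequence is modest: added noise if the missing arm is random, and bias in the mean only if one arm is preferentially missing, which the documents do not show. It would be most visible in the small Week 24 entry groups. The change should be made because it is cheap and the averaged results otherwise do not consistently measure change in the same limbs.

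**What to change.** Replace the fallback in SAP 8.2.1 with two rules:
1. For by-visit levels and the slope models, set the two-arm average to missing unless both arms are present at that visit.
2. For change-from-baseline tables and figures, compute change within each arm, with the baseline chosen per arm, and average over the arms observed at both that baseline and the visit.

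Reporting the number of one-arm records by visit would show whether the issue arose in practice.

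The cost is two sentences and one derivation change, with no new data. There will be fewer averaged records, and the averaged level is lost at any visit with one arm; the per-arm analyses keep those data. Levels and changes may have different denominators and need not subtract to one another, so the tables should show both. A change based on one matched arm is still that arm's change and not a two-arm mean. If the weaker arm were preferentially missing, requiring both arms would drop those visits selectively, which is a further reason to report the counts.
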